INVESTIGATIONAL PRODUCT: EDTA Eye Drops (EED)

PROTOCOL DATE 10 MAR 2023

AND VERSION: 6

INVESTIGATOR: [name]

INVESTIGATIVE SITE:
Department of Dermatology
University of Utah
Murray, UT

INVESTIGATOR CONTACT Office [contact]

Email: [contact]

PROTOCOL SYNOPSIS

Title	A Randomized, Efficacy Assessor-Blinded, Parallel Group, Pilot Study to Assess Preliminary Efficacy and Safety of EDTA Eye Drops (EED) v. an Active Comparator in the Suppression of Herpes Simplex Virus Eruptions in Subjects with a History of Herpes Labialis
Objective	To collect preliminary efficacy and safety data on the use of EED in subjects with a history of herpes labialis, following UV Radiation.
Introduction & Rationale	
Herpes simplex virus (HSV) infections are common and can cause significant morbidity both at the time of the original infection and when recurrences occur. There are two types of HSV – HSV-1 and HSV-2. HSV-1, the most common cause of oral “cold sores,” is transmitted mainly by oral-to-oral contact. Genital herpes is usually caused by HSV-2, although HSV-1 can also cause genital breakouts. Both HSV-1 and HSV-2 infections are lifelong, with the virus living in the ganglia of nerves that supply the area of the original infection and recurring sporadically in the same area of that nerve’s innervation. Most infections and recurrences are asymptomatic, but infectious viral shedding can occur. Patients who are not asymptomatic can develop prodromes of tingling, pain or paresthesia, and eventually blisters and ulcerations with pain. Healing generally occurs within 10 to 19 days after onset in primary infection or within 5 to 10 days in recurrent infection. Lesions usually heal completely, but recurrent lesions at the same site may cause atrophy and scarring.
 
According to WHO, in 2012 an estimated 3.7 billion people under age 50 (67%) had HSV-1 infection globally. Some patients have predictable outbreaks after exposure to noxious stimuli, such as sunlight fever, menstruation, or stress. HSV-1 can cause ocular HSV as well as dermal HSV eruptions.
 
Researchers have found that calcium signaling is involved in the translocation of the virus from the ganglia to the eruption site. It has been found that an increase of calcium levels in the extracellular matrix will precipitate the calcium signaling events that are causal to the migration of the HSV virus from the proximal ganglia to the eruption site. (Hunsperger 2003, Cheshenko 2003) Further, Husperger found in her experiments (in vitro) that the chelation of calcium greatly reduced the reactivation of the HSV virus.
 
EED, which consists of a calcium chelator and a permeation enhancer could be one such intervention. Livionex has had some anecdotal evidence that this intervention could work at preventing an HSV eruption and preventing post prodromal viral shedding.
 
IRB-approved clinical studies of HSV-1 have been performed in normal human volunteers with a history of HSV-1, who develop recurrences with prodromes after exposure to UV light. We will use this technique to induce recurrences in susceptible, HSV-1 infected individuals then treat with EED or a Comparator 5 times daily.


	
Abreva® has been chosen as the Comparator product in this study because it is approved by the FDA for treatment of HSV-related cold sores. Dosing 5 times/day has been selected as the dosing regimen because that is the dosing regimen approved for Abreva by FDA. The manufacturers of Abreva recommend that subjects not be treated for greater than 10 days. A maximum of 7 days treatment with study product has been chosen for this study. Thus, treatment in both groups of subjects, will be 5 times daily and will last until healing of the lesion, or up to 7 days following the onset of the prodrome.
 
EED is currently being used at the University of Rochester, NY. Furthermore the 2.6% EDTA eye drops have been used in a Phase I/II study under IND 70,467.

Endpoints	
Primary Efficacy Endpoint
 
• Proportion of subjects using EED v. those using the Comparator, who do not progress to Stage 3 (vesicle) of a herpes labialis outbreak following UV radiation exposure. 
Secondary Efficacy Endpoints
 
• Pain in the lip and surrounding area• Duration of lesion until healed (loss of hard crust)• Cumulative lesion area (sum of all lesions)• Maximum lesion size (size of the largest lesion) 
Safety Endpoint
 
• Adverse Events
Subjects	
Planned Enrollment
 
We will enroll until we have 20 subjects that have expressed a lesion from the induction and complete the treatment period of the study.
 
Study Entry Criteria
 
Inclusion Criteria
 
To be eligible for enrollment, a subject must meet the following criteria:
 
1. Understands the requirements of the study and provides written informed consent prior to undergoing any study-related procedures.2. Subject is a male or female between the ages of 18-80 years old, inclusive.3. Fitzpatrick skin type II or III.4. History of at least one year of herpes labialis induced by UV exposure.5. Able to recall exact location of most common or most recent outbreak.6. History of at least 50% of cold sore outbreaks occurring with UV (sun) exposure.7. At least 1 HSV-1 outbreak within the past 12 months.8. Experiences prodromal symptoms before HSV-1 outbreaks.

	
9. Subject is willing and able to comply with protocol-specified dosing, visits to the clinic and tracking of pain.
 
Exclusion Criteria
 
Subjects will be excluded from the study if they meet any of the following criteria:
 
1. Outbreak <2 weeks prior to enrollment.2. History of herpes simplex vaccine.3. On antiviral suppression within the past 30 days.4. Requires more than acetaminophen for pain for recurrent HSV outbreaks.5. On any systemic or topical steroid, immune suppressant, or chemotherapeutic agent within the past 14 days.6. Use of tanning beds, history of sunburn, or beach vacation <2 weeks prior to enrollment.7. History of photosensitivity, lupus erythematosus, or current use of photosensitizing medication.8. Current immunosuppressed state due to underlying disease (i.e. HIV infection) concomitant treatment (i.e. chemotherapy).9. Current upper respiratory tract infection or any active illness that could trigger cold sores or affect overall health of the patient or the assessment of the study product.10. Pregnant or intending to become pregnant during the study.11. Abnormal skin conditions in the area of the recurrent HSV1 outbreaks.12. Enrolled in another clinical trial within the past 30 days.13. Previously treated with EED.14. On any analgesics or NSAIDs that cannot be stopped during the study.15. Alcohol or drug abuse.
Design	
This will be a randomized, efficacy assessor-blinded, parallel group, pilot study of up to 20 subjects with documented MED induced herpes labialis.
 
Potential subjects will be assessed during a screening visit that must take place no greater than 2 weeks prior to the lesion induction visit. During the screening period, subjects that meet all other entry criteria will undergo UV susceptibility testing to determine their individual MED (minimal erythema dose). UV susceptibility testing takes place over two days with exposure to UV light on specified regions on the subject's back followed by an assessment of the exposed areas 24 hours later to identify the MED. Subjects who have a measurable MED will be allowed to continue to the induction visit. Patients that do not have a measurable MED response will be considered screen failures or they may have repeat MED testing with different levels.
 
At the Induction Visit, subjects will undergo UV radiation at a level 3 times their MED. The exposed area of the lip will be marked with indelible ink and a photograph may be taken. Each subject will then be randomly assigned in a 1:1 ratio to receive either EED or Comparator. Subjects will be dispensed

	
study medication and instructed how to apply it to the exposed area. When the patient first senses the start of developing a cold sore and applies study medication will be considered Day 1. Dosing of the study product will be done five times daily, beginning at the time that a subject first senses the start of the prodromal phase (Day 1). Subjects will be given a diary card to record their pain levels, progression of lesion development and any unusual symptoms (not normally seen with their outbreaks).
 
Patients will be called daily by the study team after their induction visit to determine the start of prodrome. If after 7 days, the patient does not develop any prodromal senses, the patient will be considered an induction failure.
 
When the patient first senses signs or symptoms of a cold sore, they will have the Day 1 visit conducted within 24 hours. Day 1 visit may be conducted in person or as a MyChart Virtual Visit. Their diary card will be reviewed and if they have experienced a prodrome and/or lesion since the induction visit, their compliance with dosing will be checked. If the subject has noted any unusual symptoms, these will be discussed with medical personnel to determine if the symptoms represent a treatment emergent AE. A photo will be taken of the irradiated area (as marked at the induction visit). The blinded assessor will assess the prodrome and/or lesion and take measurements.
 
On Days 3, 5, and 7, the subject will return to the clinic or follow up via virtual video call for assessment of the irradiated area. Study staff will review the subject diary to determine if the subject is correctly noting the lesion stage. Subjects will have a photo taken of the radiated area and asked to continue with dosing as instructed. Any diary card notation of unusual symptoms in subjects will be reviewed by study staff to determine if the symptoms represent a treatment emergent adverse event. The blinded assessor will assess the prodrome and/or lesion and take measurements. More study product may be dispensed as needed. Most subjects' lesions will have resolved by day 7, and they will end study treatment after 7 full days of treatment. If lesion has not resolved by day 7, the maximum number of days the patient may use study drug treatment is 10 days.
 
The EOS is the final study visit will take place on Day 10. A photo will be taken of the irradiated area, the diary card will be carefully reviewed and study product (including empty containers) will be collected. If subjects reach EOS without full resolution of their lesion(s), they will be given the option to begin taking a prn medication for the remainder of the outbreak. Measurements will be taken. If an adverse event has occurred but has not resolved by the EOS visit, the subject will be contacted once weekly and status noted until such time as the event has resolved. The blinded assessor will assess the prodrome and/or lesion.
 
A Safety follow-up phone call will occur 2 days after the EOS to determine if any new AEs have occurred.
 
Safety will also be evaluated by an independent physician throughout the study. The first independent safety evaluation will be done once 5 subjects

--	--

[figure not shown]
	have reached EOS. Thereafter, the independent safety evaluation will occur as each subsequent group of 5 subjects reaches EOS and will include data on all subjects having reached EOS.
Enrollment Period	Subjects will be enrolled over a 2 year period.
Treatment Period	Subjects will be treated for up to 7 days from the time they first experience a prodrome and/or a lesion. If lesion has not resolved by day 7, the maximum number of days the patient may use study drug treatment is 10 days. If subjects reach EOS without full resolution of their lesion(s), they will be given the option to begin taking a prn standard of care medication for the remainder of the outbreak. Subjects that do not exhibit a prodrome within 7 days of the induction visit, will be considered induction failures and be discharged from the study. Total time of study participation for any given subject may range from 13 to 25 days.
Location	University of Utah MidValley Clinic, Department of Dermatology
Safety Assessments	Solicited AEs by review of diary cards and discussion with subjects
Efficacy Assessments	Primary: 
Number of subjects that experience prodrome (Stage 1) but do not progress to vesicles (Stage 3) by completion of treatment Secondary: 
Subject-assessed duration of painClinician-assessed duration of lesion appearance (Stage 3), as reported by subject, to complete healing (Stage 5)Measurement of cumulative lesion area (all eruptions if more than 1)Measurement of each lesion (if more than one) from eruption (Stage 3) through healing of hard crust (Stage 4) to identify the largest lesion

TABLE OF CONTENTS

PROTOCOL SYNOPSIS	ERROR! BOOKMARK NOT DEFINED.
1. INRODUCTION	1
1.1 Background and Rationale	1
2. OBJECTIVE	2
2.1 Efficacy Endpoints	2
2.1.1 Primary:	2
2.1.2 Secondary:	2
2.2 Safety Endpoint	2
3. STUDY DESIGN	2
4. STUDY TREATMENT	4
4.1 EDTA Eye Drops	Error! Bookmark not defined.
4.2 Comparator: Abreva®	4
4.3 Randomization Codes	4
5. SUBJECT POPULATION	4
5.1 Inclusion Criteria	4
5.2 Exclusion Criteria	5
6. STUDY PROCEDURES	6
6.1 Study Visits	6
6.1.1 Screening Visit (Days -14 to 0)	6
6.1.2 Study Day 1 Visit (Baseline)	Error! Bookmark not defined.
6.1.3 Study Days 3 and 5 Visits	8
6.1.4 Study Day 7 +/- 1 day Visit	8
6.2 Study Day 10 Visit	Error! Bookmark not defined.
6.2.1 End of Study (EOS) Visit	Error! Bookmark not defined.
6.3 Early Discontinuation Visit	9
7. EFFICACY EVALUATIONS	9

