Abreva® has been chosen as the Comparator product in this study because it is approved by the FDA for treatment of HSV-related cold sores. Dosing 5 times/day has been selected as the dosing regimen because that is the dosing regimen approved for Abreva by FDA. The manufacturers of Abreva recommend that subjects not be treated for greater than 10 days. A maximum of 7 days treatment with study product has been chosen for this study.

Thus, treatment in both groups of subjects, will be 5 times daily and will last until healing of the lesion, or up to 7 days following the onset of the prodrome.

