3. STUDY DESIGN

This will be a randomized, efficacy assessor-blinded, parallel group, pilot study of up to 20 subjects with documented UV induced herpes labialis. We will enroll until we have 20 subjects that have expressed a lesion from the induction and complete the treatment period of the study. With the possibility of screen failures and induction failures, we may consent up to 35 patients maximum.

Potential subjects will be assessed during a screening visit that must take place no greater than 2 weeks prior to the Induction visit. During the screening period, subjects that meet all other entry criteria will undergo UV susceptibility testing to determine their individual MED (minimal erythema dose). UV susceptibility testing takes place over two days with exposure to UV light on specified regions on the subject's back followed by an assessment of the exposed areas 24 hours later to identify the MED.

Subjects who have a measurable MED will be allowed to enroll in the study. Each subject will be randomly assigned in a 1:1 ratio to receive either EED or Comparator.

Subjects that do not have a measurable MED will be considered screen failures or may have repeat MED testing with new values.

At the Induction Visit, subjects will undergo UV radiation at a level 3 times their MED. The exposed area of the lip will be marked with indelible ink and a baseline photograph may be taken.

Each subject will then be randomly assigned in a 1:1 ratio to receive either EED or Comparator. Subjects will be dispensed study medication and instructed how to apply it to the exposed area. Dosing of the study product will be done 5 times daily, beginning at the time that a subject first senses the start of the prodromal phase (Day 1). The EED is a clear viscous eye drop, and the Comparator is a white cream substance. Therefore, the subject and principal investigator will be unblinded, and only efficacy assessments will be done by a qualified trained blinded assessor.

Subjects will be given a diary card to record their pain levels (starting at Day 1), progression of lesion development and any unusual symptoms (not normally seen with their outbreaks).

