5.2 Exclusion Criteria

Subjects will be excluded from the study if they meet any of the following criteria:

1. Outbreak <2 weeks prior to enrollment.
2. History of herpes simplex vaccine.
3. On antiviral suppression within the past 30 days.
4. Requires more than acetaminophen for pain from recurrent HSV outbreaks.
5. On any systemic or topical steroid, immune suppressant or chemotherapeutic agent within the past 14 days.
6. Use of tanning beds, history of sunburn, or beach vacation <2 weeks prior to enrollment.
7. History of photosensitivity, lupus erythematosus, or current use of photosensitizing medication.
8. Current immunosuppressed state due to underlying disease (i.e. HIV infection) concomitant treatment (i.e. chemotherapy).
9. Current upper respiratory tract infection or any active illness that could trigger cold sores or affect overall health of the patient or the assessment of the study agent.
10. Pregnant or intending to become pregnant during the study.
11. Abnormal skin conditions in the area of the recurrent HSV1 outbreaks.
12. Enrolled in another clinical trial within the past 30 days.
13. Previously treated with EED.
14. On any analgesics or NSAIDs that cannot be stopped during the study.
15. Alcohol or drug abuse.

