6. STUDY PROCEDURES

6.1 Study Visits

6.1.1 Screening Visit (Days -14 to 0)

No more than 14 days prior to their planned start of study, subjects will report to the dermatology clinic for the following screening procedures:

- Presentation, review and signing of the informed consent.
- Review of their medical history.
- Review of HSV history.
- Assist with setting up MyChart account.
- Review of Inclusion and Exclusion criteria.
- Limited Physical Exam – to ensure that there are no co-morbidities that may interfere with study compliance or results.
- Notation of any concomitant medications the subject is currently taking (and that do not conflict with entry criteria).

ONLY IF the subject meets all entry criteria and is considered by the Investigator to be able to comply with and complete all study procedures, may they proceed to the final screening procedure of UV Susceptibility and Calculation of MED (refer to Study Manual for detailed instructions) consisting of:

- Exposure to UV Radiation.
- Assessment of Exposed Area – no more than 24 hours after exposure.

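### The entry criteria exclude prior EED use but not a known hypersensitivity or intolerance to an ingredient of EED or to Abreva

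*Combined protocol and SAP*

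**What the plan says.** The synopsis and section 5.2 carry the same 15 exclusions. Only one concerns experience with a study product: "Previously treated with EED". The nearest other items are "On antiviral suppression within the past 30 days" and "Abnormal skin conditions in the area of the recurrent HSV1 outbreaks".

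Section 4.1 describes EED as 2.6% EDTA with MSM as permeation enhancer. Section 1.1 says Abreva was chosen because "it is approved by the FDA for treatment of HSV-related cold sores". Section 4.3 allocates subjects 1:1 by a simple randomisation code. Section 3 has the product applied to the area of the lip irradiated at 3 x MED, five times daily from prodrome, and states that "the subject and principal investigator will be unblinded", with efficacy ratings by a blinded assessor.

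At screening (section 6.1.1) staff review medical history, perform a limited physical exam and carry out a "Review of HSV history". UV testing then follows "ONLY IF the subject meets all entry criteria and is considered by the Investigator to be able to comply with and complete all study procedures".

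**The concern.** A trial that applies one of two topical products to freshly irradiated skin would normally exclude people known to react to either. Here the written criteria deal with past exposure to one product only, and for that product only with the finished formulation. Two kinds of subject pass through: someone with a past reaction to Abreva, and someone who has never used EED but has reacted to EDTA or MSM in another product.

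The first stake is safety, since exposure of such a subject could be avoided. The second is measurement. The primary endpoint depends on telling whether a lesion at the irradiated site has reached the vesicle stage, and a product reaction at that site is a further source of confusion. Section 6.1.4 already accepts that a lesion could be mistaken, because it provides for swabs to separate a cold sore from a reaction to the UV exposure.

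**Working it through.** There is no figure in the plan to reproduce on this point. The check is a comparison of provisions, followed by short arithmetic.

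**1. Does any provision exclude a subject with a known reaction?**

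| Provision | What it covers | Excludes a known reaction to EDTA, MSM or Abreva? |
|---|---|---|
| Exclusion 3 | Antiviral suppression in the past 30 days | No: recent use, not tolerance |
| Exclusion 7 | Photosensitivity, lupus, photosensitising drugs | No: reaction to light, not to a product |
| Exclusion 9 | Current infection or active illness | No: a past reaction is not an active illness |
| Exclusion 11 | Abnormal skin at the outbreak site | No: skin may be normal at entry |
| Exclusion 13 | Any prior EED treatment | Only a reaction to EED itself |
| Inclusion 9 | Willing and able to follow dosing and visits | Not by its terms; a subject may decline |
| 6.1.1 history and limited exam | Medical and HSV history; co-morbidities affecting compliance or results | May bring the reaction to light; no rule acts on it |
| 6.1.1 Investigator check | That the subject "is considered by the Investigator to be able to comply with and complete all study procedures" | Not by its terms; tolerance of the product is not named |

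No row excludes such a subject outright.

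**2. Chance of exposure.** With 1:1 simple randomisation, a subject who reacts to one of the two products receives it with probability 1/2. If k such subjects are randomised, the chance that at least one receives the product in question is 1 − 0.5^k:

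- k = 1: 1 − 0.5 = 0.50
- k = 2: 1 − 0.25 = 0.75
- k = 3: 1 − 0.125 = 0.875

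The documents give no basis for k; these values are assumptions.

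**3. Weight of one misrated lesion.** Enrolment runs until 20 subjects complete, which is 20/2 = 10 per arm if allocation is balanced. One subject whose reaction is rated as a vesicle changes that arm's proportion by 1/10 = 10 percentage points. The shift counts against whichever product caused the reaction.

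**4. Prior Abreva experience, a separate question.** Assume that EED succeeds in 0.40 of subjects and that Abreva does the same in subjects with no known history of response. Let a share f be known Abreva failures (success 0) and a share g be known Abreva responders (success 0.80). Abreva-arm success is then 0.80g + 0.40(1 − f − g).

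| f | g | Abreva arm | EED minus Abreva |
|---|---|---|---|
| 0.20 | 0 | 0 + 0.32 = 0.32 | +8 points |
| 0.20 | 0.20 | 0.16 + 0.24 = 0.40 | 0 |
| 0.20 | 0.40 | 0.32 + 0.16 = 0.48 | −8 points |
| 0 | 0.20 | 0.16 + 0.32 = 0.48 | −8 points |

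All rates and shares in this table are assumed. It shows only that the sign depends on the mix of past failures and past responders enrolled, on which the documents are silent.

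**The case against.** The best defence is that ordinary screening would catch these subjects. Both products are identified to the subject, who is not blinded. A person who has reacted to Abreva may be unwilling to accept dosing with it and so fail inclusion 9. Medical history is reviewed, and the Investigator must judge that the subject can complete the study. A past reaction to EED itself is already covered by exclusion 13. All of this makes the event less likely. None of it makes the subject ineligible: history-taking without a rule leaves the decision to individual judgement, and a subject may not know that EED contains an ingredient they have reacted to.

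On measurement, a blinded assessor rates the lesion, and an HSV swab could separate a cold sore from a local reaction. Blinding does not by itself tell a reaction from a vesicle, though. Under section 6.1.4 swabbing is optional, is omitted at weekends and is reserved for the first five patients, with extension to all only a possibility. The defence reduces this part of the concern without removing it.

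Finally, this is a 20-subject pilot meant to give preliminary data. That limits the inferential weight of any effect on the comparison, but it is not a reason to leave out a safety exclusion.

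**Conclusion.** The gap is real and follows from the text alone. Neither exclusion list bars a subject with a known hypersensitivity or intolerance to EDTA, MSM or Abreva, and no other provision does so by its terms. If such a subject reacts to one of the products, the chance of being assigned it is 1 in 2. How many would present cannot be estimated from the documents. The measurement effect is possible rather than shown: 10 points on one arm per misrated subject, assuming about 10 per arm.

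A reader might go further and infer that barring EED-experienced subjects while admitting past Abreva failures tilts the comparison towards EED. The documents do not support that. Known Abreva responders are admitted on the same terms, and the table above gives gaps of +8, 0 or −8 points depending on assumed shares. Randomisation balances prior response between arms in expectation, so the issue is which population the contrast describes, plus chance imbalance in small arms; it is not confounding. Nor does the hypersensitivity gap have a direction, since a reaction to EDTA or MSM would count against EED. Subjects in both arms know their treatment, so expectation can colour self-reports in either arm.

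**What to change.** Add one item to the exclusion lists in section 5.2 and the synopsis: known hypersensitivity or intolerance to any ingredient of EED or Abreva. The existing medical history review can carry the question. The cost is one line in each list and a slightly smaller eligible pool.

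Optionally, record prior Abreva use and response in the HSV history already taken and show both by arm in the baseline table. This changes no result, but it lets a reader see who was enrolled. The cost is one question and a row or two.

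The exclusion should not be widened to subjects who say Abreva did not work for them. Removing self-reported failures while keeping self-reported responders is itself a one-sided selection: the last row of the table (no failures, 20% responders) gives 8 points towards Abreva under the stated assumptions. Whether to study all comers is a choice of target population for the sponsor to state.
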